### **1.3 Potential Risks and Benefits**

#### **1.3.1 Potential Risks**

Some patients may experience anxiety or claustrophobia but this would likely be to a lesser degree than the thermoplastic mask in which they receive daily radiation treatments. Some patients may experience mild discomfort with the strap application to their foreheads and chins.

CBCTs are used in a regular basis for set up verification and deliver small amounts of additional radiation.

Rationale for additional imaging: No patient will receive radiation treatment with the experimental MID. Patient setup reproducibility and accuracy will be assessed by CBCT. Each day a patient is treated with radiation treatment, they are positioned to replicate the patient setup on the day the CT for radiation treatment planning was obtained. To verify this setup, images such as CBCTs can be obtained and compared to the original CT simulation scan. Since CTs are three dimensional, translational setup errors in the X, Y and Z axis can be quantified.

We need to obtain two additional setup CBCTs on two different treatment days. The CBCT with the MID will allow us to compare the MID setup with the CT simulation scan. The CBCT with the thermoplastic mask will allow us to assess setup error of the gold standard compared to the CT simulation scan. We can then compare the error of the thermoplastic mask with the experimental MID. **Patient safety and treatment will not be compromised as no treatments will be delivered with the MID.**

Safety of additional imaging: CBCTs are obtained by kV imaging. Each CBCT is approximately 5 cGy. The 4 additional CBCTs will add approximately 20 cGy to the patients overall radiation exposure. Patients receiving RT for primary brain tumors will be treated with 300x this dose (6000 cGy). Patients receiving radiation for head and neck cancers may receive doses of 6000-7000 cGy. Patients receiving RT for secondary/metastatic intracranial malignancies will receive 150x this dose (3000 cGy). Thus this additional imaging poses little if any risk to the patient and can ensure more accurate treatment setup and radiation delivery.

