#### 2.2.3 Exploratory

## 3 Study Design

This is a single-institution, pilot study using a MID for RT treatment immobilization of patients being treated for head and neck cancers or intracranial tumors who require radiation therapy.. The patient population will be outpatient based, all of them receiving RT to treat head and neck cancers or intracranial tumors, assessed by CBCT and patient QOL surveys over the duration of their radiation treatment. There will only be a single study arm in which all patients receive RT with the thermoplastic mask but also receive CBCT imaging with the MID to assess the setup accuracy and reproducibility. Patient tolerance of the MID will be assessed through a survey delivered the day of MID use. Setup accuracy will be evaluated by comparing translational shifts required with MID to shifts required with thermoplastic mask. The last QOL evaluation will be at the completion of the patient's radiation treatment. **No radiation therapy will be delivered with MID immobilization.**

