# 6 Study Schedule

CT simulation	Port films	Fraction A	Fraction B
Day 1	Day 8	Day 8 ± 5	Day 15 ± 5
Thermoplastic mask immobilization	Thermoplastic mask immobilization + CBCT	Thermoplastic mask immobilization + CBCT	Thermoplastic mask immobilization + CBCT
		RT*	RT*
MID		MID + CBCT	MID + CBCT

\*RT is standard of care and will only be given while patients are immobilized with the standard thermoplastic mask.

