## 11 Statistical Considerations

### 11.1 Study Hypotheses

**Primary objective:** To establish that the new device is no worse than the old device in term of the setup accuracy and reproducibility. Accuracy will be measured by quantifying the difference in translational shifts from the daily setup to planning CT scan digitally reconstructed radiograph (DRR). The magnitude of shifts will be compared to the shifts required using the gold standard thermoplastic mask.

**Secondary objective:** To establish that the new device is no worse than the old device in term of increasing patients' comfort and reduce patients' anxiety. The measurable outcome will be a questionnaire that assesses the patient's pain, discomfort and level of anxiety when in the MID compared to when in the thermoplastic mask.

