### 11.2 Analysis Plans

For the primary objective, the magnitude of the single vector that depicts the degree of setup discrepancy from CT simulation will be collected for each patient on each day the MID is applied (for both the thermoplastic mask and the MID). The 90% lower

confidence limit of the absolute discrepancy, as well as the 90% higher confidence limit of the standard error, will serve as a conservative estimate of the mean and standard deviation. Based on literature, the thermoplastic mask results in a need for translational shifts on average of 3.5mm with a standard deviation of 1.2mm. We propose to use a total of 24 patients in the pilot study aiming to establish that the new device is no worse than the old device with a non-inferiority margin of 0.5mm, assuming the new device requires a mean translational error adjustment of patients by 2.5mm with the standard deviation of 1.2mm at 91% power and a Type-I-Error rate of 5%.

For the secondary objective, we will collect the preference survey scores for the thermoplastic mask versus the MID (survey results) from the same patients participated in the primary objective. The preference scores will be compared using cumulative logistic regression model.

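### The 91% power in section 11.2 is not the power of the paired design: on the plan's own inputs 24 paired patients give about 99.5% or more, and no power is given for equal devices

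*Combined protocol and SAP*

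**What the plan says.** Section 11.1 sets the primary aim: "To establish that the new device is no worse than the old device in term of the setup accuracy and reproducibility". Section 11.2 takes from the literature that "the thermoplastic mask results in a need for translational shifts on average of 3.5mm", with an SD of 1.2 mm, and sets a 0.5 mm margin. Its power is computed "assuming the new device requires a mean translational error adjustment of patients by 2.5mm with the standard deviation of 1.2mm at 91% power", with a type I error rate of 5%. Sidedness, the test and the SD of the within-patient difference are not stated. Section 11.3 only refers back to section 11.2, so this is the whole sample size justification.

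The design is described elsewhere. Section 3 has "a single study arm in which all patients receive RT with the thermoplastic mask but also receive CBCT imaging with the MID". Section 11.2 says the setup vector "will be collected for each patient on each day the MID is applied (for both the thermoplastic mask and the MID". The section 6 table lists "Thermoplastic mask immobilization + CBCT" and MID with CBCT under both Fraction A and Fraction B. Section 1.3.1 gives the purpose of imaging on two treatment days as comparing the error of the two devices.

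Specific Aim 1 in section 1.2 expects the two devices to have much the same error. It does not predict that the MID will be better.

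**The concern.** Each of the 24 patients supplies both a mask value and a MID value. Power then depends on the SD of the within-patient difference, which the plan does not give, and on how the two days are combined, which it does not say. A single power figure built from per-device SDs suggests a calculation for separate groups.

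The figure also rests on the MID being 1.0 mm better than the mask (2.5 against 3.5 mm). The mask value has a literature source; the MID value has none. With a 0.5 mm margin, the assumed advantage supplies two thirds of the 1.5 mm between the assumed truth and the margin. If the devices are equal, only 0.5 mm remains. A reader who sees 91% power beside a claim of being no worse could take an inconclusive result as evidence against the MID, when the study may simply have had little power in that case.

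**Working it through.** **Inputs from section 11.2:** 24 patients; margin 0.5 mm; mask mean 3.5 mm; MID mean 2.5 mm; SD 1.2 mm per device; type I error 5%. The distance from the assumed truth to the margin is 0.5 + (3.5 − 2.5) = 1.5 mm. With equal devices it is 0.5 mm.

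**Assumed, because the documents give no value:** within-patient correlation r between the two devices, from 0 to 0.7.

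Power is the probability that a noncentral t variable with noncentrality λ exceeds the one-sided critical value.

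**1. Reproducing 91%.** Two independent groups of n have λ = distance / (1.2 × √(2/n)) and 2n − 2 degrees of freedom.

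- 12 per group: λ = 1.5 / (1.2 × √(2/12)) = 3.06. Power is 90.7% at one-sided 5% (92.2% by the normal approximation) and 83.3% at one-sided 2.5%.
- 24 per group: 99.6% at one-sided 5% and 98.9% at one-sided 2.5%.

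Dropping the margin and using a 1.0 mm distance with 24 per group gives 88.5% (normal 89.3%), a poorer match. Twelve per group at one-sided 5% is the closest reading.

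**2. The paired design on the plan's inputs.** With one value per device, the SD of the difference is s = 1.2 × √(2(1 − r)), λ = distance × √24 / s, and there are 23 degrees of freedom. At r = 0, s = 1.697 and λ = 1.5 × 4.899 / 1.697 = 4.33.

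| r | s (mm) | MID 1.0 mm better, one-sided 5% | same, one-sided 2.5% |
|---|---|---|---|
| 0 | 1.697 | 99.47% | 98.5% |
| 0.3 | 1.420 | 99.96% | 99.9% |
| 0.5 | 1.200 | >99.9% | >99.9% |
| 0.7 | 0.930 | >99.9% | >99.9% |

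Averaging the two days would only raise these. At one-sided 5%, 24 pairs have 91% power on these inputs only if s = 2.39 mm, that is r = 1 − 2.387² / 2.88 = −0.98. Even at r = −0.5, power is 96.3%. At r = 0, 13 pairs reach 91%.

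**3. Equal devices (distance 0.5 mm).** Averaging two fully independent days halves the variance of the difference. If the two days' differences correlate at 0.5, the variance is multiplied by (1 + 0.5)/2 = 0.75.

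| Power at equality | r = 0 | 0.3 | 0.5 | 0.7 |
|---|---|---|---|---|
| One value per device, one-sided 5% | 40% | 51% | 63% | 82% |
| Two days averaged, day differences correlated 0.5, one-sided 5% | 49% | 61% | 74% | 90% |
| Two days averaged, independent (best case), one-sided 5% | 63% | 76% | 88% | 98% |
| One value per device, one-sided 2.5% | 28% | 38% | 50% | 71% |
| Two days averaged, independent, one-sided 2.5% | 50% | 65% | 79% | 95% |

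At equality and one-sided 5%, power reaches 91% only if the SD of the analysed difference is about 0.80 mm or less. That means r of about 0.78 with one value per device (1 − 0.796² / 2.88), or 0.56 with two independent days averaged (1 − 0.796² / 1.44).

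**The case against.** The strongest objection comes from section 11.2 itself. Just before the power statement, it says that 90% confidence limits of the discrepancy and of its standard error will be used as conservative estimates of the mean and SD. If these were power inputs, a paired calculation could land near 91%. Take 24 pairs and one-sided 90% limits: reduce the distance to 1.5 − 1.319 × s/√24 and multiply the SD by √(23/χ²) = 1.245, where χ² is the 10th percentile on 23 degrees of freedom. At r = 0.3 this gives 91.3%.

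This does not rescue the figure. That sentence looks ahead to data still to be collected, and the power statement names its own inputs of 3.5, 2.5 and 1.2 mm. The match also depends on the chosen correlation: the same adjustment gives 75.9% at r = 0 and 98.2% at r = 0.5. The statement that 91% requires r = −0.98 applies to the stated inputs without such adjustment.

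Other points stand in part:

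- **The arithmetic is right for another layout.** The fault is a mismatch with the design, and on the plan's inputs it does no harm to the sample size.
- **Powering at an expected advantage is legitimate.** The plan discloses the 2.5 mm as an assumption, and neither Aim 1 nor section 11.1 fixes a true difference of exactly zero. But no basis for the 2.5 mm is given, and near-equality is what Aim 1 expects.
- **The equality figures rest on an unknown correlation.** Each device has its own CT simulation (section 6.3 and Appendix A), so a positive correlation cannot be taken for granted. The figures show how strongly power depends on an unstated quantity; they do not estimate it.
- **This is a pilot.** Even so, the plan sets a margin, a power and an error rate in order to establish non-inferiority, so these should describe the study being run.

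**Conclusion.** The concern holds. The stated 91% is not the power of 24 patients each measured with both devices. On the plan's own inputs that power is 99.5% (99.47% unrounded) or more at one-sided 5%, and 98.5% or more at one-sided 2.5%, for any correlation of 0 or above. That the 91% came from two groups of 12 is an inference, but the conclusion does not depend on it: 24 unpaired values per device also give 99.6%.

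The understatement is in the safe direction and gives no reason to change the sample size. The substantive gap is at equality. Across the correlations, sidedness and ways of combining days considered above, power there runs from 28% to 98%, and the plan gives none of the three quantities needed to place the study in that range. The plan should be corrected, but the point does not invalidate the design.

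**What to change.** Keep 24 patients. In section 11.2, replace the 91% with power for the paired design at two true differences, a 1.0 mm MID advantage and zero. State:

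- whether the 5% is one-sided;
- whether the two fractions are averaged, modelled or analysed singly;
- the assumed SD of the within-patient difference, kept distinct from the 1.2 mm per-device SD, with the correlation it implies;
- the basis for the 2.5 mm MID mean, or that there is none beyond assumption.

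Possible wording, with the correlation as a placeholder for the team's own choice:

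> Each of 24 patients is measured with both devices. With one value per device per patient, a one-sided 5% test, a 0.5 mm margin, a per-device SD of 1.2 mm and an assumed within-patient correlation of 0.5 (SD of the difference 1.2 mm), power is over 99% if the MID is 1.0 mm better and 63% if the devices are equal. At equality it ranges from 40% to 82% for correlations from 0 to 0.7.

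If the fractions are averaged, say so and give the matching figures (63% to 98% at equality with fully independent days, one-sided 5%).

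The cost is wording only, with no extra patients. The team must commit in advance to sidedness, a within-patient SD and a rule for the two fractions, and must print a power at equality that may look less favourable than 91%.

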### **6.3 Treatment Period**

Visit 1, Day 1

CT simulation with thermoplastic mask. CT simulation with MID. Survey for anxiety and comfort. Symptom directed physical examination. Record any adverse events.

Visit 3, Day 8 ± 5

MID application and setup verification with CBCT. Survey for anxiety and comfort. Symptom directed physical examination. Record any adverse events.

Visit 4, Day 15 ± 5

MID application and setup verification with CBCT. Survey for anxiety and comfort. Symptom directed physical examination. Record any adverse events.

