### Emotional Distress-Anxiety

Please respond to each item by marking one box per row.

In the past 7 days...

		Never	Rarely	Sometimes	Often	Always
		1	2	3	4	5
EDANX27	I felt something awful would happen .....					
EDANX28	I felt uneasy .....					
EDANX29	I felt anxious.....					
EDANX30	I felt upset.....					
EDANX31	I had difficulty calming down .....					
EDANX32	I felt fearful.....					
EDANX33	I felt frightened.....					
EDANX34	I felt terrified.....					
EDANX35	I was concerned about my mental health .....					
EDANX36	I felt indecisive .....					
EDANX37	I had sudden feelings of panic .....					
EDANX38	I felt fidgety .....					
EDANX39	I felt like I needed help for my anxiety ....					

PROMIS - Ca Item Bank v1.0 - Emotional Distress - Anxiety

In the past 7 days...

	Never	Rarely	Sometimes	Often	Always	
	1	2	3	4	5	
EDANX00	I felt worried.....					
EDANX04	I felt nervous.....					
EDANX01	I had trouble relaxing.....					
EDANX06	I felt tense.....					
EDANX01	My worries overwhelmed me.....					
EDANX00	It scared me when I felt nervous.....					
EDANX06	Many situations made me worry.....					
EDANX05	I had unpleasant thoughts that wouldn't leave my mind.....					
EDANX09	I worried about dying.....	

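### The secondary no-worse aim for comfort and anxiety has no margin on the survey scale, and the cumulative logistic model named for repeated scores from the same patients has no patient term

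*Combined protocol and SAP*

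**What the plan says.** The secondary objective in section 11.1 begins "To establish that the new device is no worse than the old device in term of increasing" comfort and reducing anxiety. Its outcome is "a questionnaire that assesses the patient's pain, discomfort and level of anxiety when in the MID compared to when in the thermoplastic mask", which reads as one rating per device.

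Section 11.2 says "we will collect the preference survey scores for the thermoplastic mask versus the MID (survey results) from the same patients", which could equally mean one comparative preference per survey. The whole of the analysis is: "The preference scores will be compared using cumulative logistic regression model". No patient effect, pairing, clustering or visit term is mentioned.

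The only margin appears in the primary analysis, "no worse than the old device with a non-inferiority margin of 0.5mm". Section 11.3 refers back to 11.2 and adds nothing for the survey.

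Section 6.3 lists "Survey for anxiety and comfort" at the Day 1, Day 8 and Day 15 visits, and the schedule in Appendix A marks the questionnaire three times. Specific Aim 2 in section 1.2 words the same question as superiority: less claustrophobia and/or anxiety with the MID.

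The only form shown is the anxiety item bank in Appendix B, with the instruction "Please respond to each item by marking one box per row". It asks about the previous seven days and names no device.

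**The concern.** There are two gaps.

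First, a no-worse conclusion needs a statement of how much worse would be acceptable. Without one, a non-significant difference in 24 patients cannot be told apart from too little information.

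Second, each patient contributes several scores, and these are correlated. A cumulative logit in its standard form counts every row as a separate subject. Its standard error then ignores two opposing effects. Pairing makes the device contrast more precise than the model believes. Patient-by-device differences that repeat over visits make it less precise. The p-value and interval may be too cautious or too optimistic, and the plan does not let the reader say which.

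**Working it through.** **The plan's own figure.** There is none for the survey. The stated 91% power with 24 patients belongs to shifts. It reproduces from a distance to the margin of 0.5 + (3.5 − 2.5) = 1.5 mm, SD 1.2 mm, two groups of 12 and one-sided 5% (90.7% by noncentral t). It carries no information about a survey score.

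**Inputs.** From the documents: 24 patients, both devices in every patient, surveys at three visits. Assumed, because the documents give no survey variances: a five-level score with latent value = patient intercept (SD τ) + device × (effect + patient-by-device slope, SD s) + logistic error with variance e = π²/3 = 3.29; two-sided 5%; nine (τ, s) settings; 4,000 simulated trials each (Monte Carlo error about ±0.7 points at 5%).

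**Why the direction depends on the layout.** With V ratings per device per patient, the true variance of the device difference is proportional to s² + 2e/V. Independent rows take it as (2τ² + s² + 2e)/V. On the latent scale the ratio of true to assumed variance is approximately

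R = (V·s² + 2e) / (2τ² + s² + 2e).

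- V = 1: R cannot exceed 1, so the standard error is never too small.
- V = 3: R = 1 when s = τ. It is below 1 when s < τ and above 1 when s > τ.

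Comparing 1/√R with the simulated ratio of model SE to true SD, at V = 3:

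- τ = 1.8, s = 0: R = 6.58/13.06 = 0.504, 1/√R = 1.41; simulated 1.35.
- τ = 1.0, s = 1.0: R = 9.58/9.58 = 1.00; simulated 1.01.
- τ = 0.5, s = 2.0: R = 18.58/11.08 = 1.677, 1/√R = 0.77; simulated 0.79.

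**Each device rated at each of three visits: type I error, %.** Clustered means the same fit with patient-clustered variance × n/(n−1) and t on 23 df. Paired means a t-test on patient-level mean differences.

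| τ, s | Independent rows | Clustered | Paired |
|---|---|---|---|
| 1.8, 0 | 0.8 | 4.6 | 4.6 |
| 2.5, 0 | 0.4 | 4.3 | 4.9 |
| 1.0, 0.5 | 3.7 | 4.7 | 5.0 |
| 1.5, 1.0 | 3.5 | 4.6 | 5.0 |
| 1.0, 1.0 | 4.8 | 4.5 | 4.7 |
| 0.5, 1.0 | 7.4 | 4.6 | 4.8 |
| 1.5, 1.5 | 5.1 | 4.7 | 4.8 |
| 1.0, 2.0 | 11.2 | 5.4 | 5.3 |
| 0.5, 2.0 | 12.0 | 4.6 | 4.5 |

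Four of the nine settings are near nominal (3.5 to 5.1%). Where the independent-rows test is conservative it also loses power. At τ = 2.5, s = 0 and a true patient-level log odds ratio of 0.8, the score-test version detects the difference in about 21% of trials, against 55% paired.

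**One rating per device per patient.** Type I error with independent rows was 0.4 to 4.7% over the same settings: conservative only, as R ≤ 1 requires.

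**One preference per visit.** Pairing is built in and only the repetition over visits remains. The design effect is 1 + (3 − 1) × ICC, with ICC = SD²/(SD² + 3.29). At patient SD 1.0, ICC = 1/4.29 = 0.233, the design effect is 1.466 and the SE is too small by a factor of √1.466 = 1.21. The implied error is 2 × [1 − Φ(1.96/1.21)], about 10.6%. Simulated errors for patient SD 0, 0.5, 1.0, 1.5 and 2.0 were 5.3, 6.4, 10.9, 13.9 and 16.2%, against 4.9 to 5.6% on patient means. These used a one-sample t-test on rows as a stand-in for the threshold-only cumulative logit.

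**What a margin would mean at n = 24.** For a paired non-inferiority test with true difference 0, one-sided 5% and 23 df, the noncentrality is margin × √24 / √(2(1 − ρ)), with the margin in SD units. For ρ from 0 to 0.7, power is 17 to 34% at 0.2 SD, 26 to 58% at 0.3 SD, 51 to 92% at 0.5 SD and 85 to 99.9% at 0.8 SD. These margins are assumptions. The missing number decides whether the aim is attainable.

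**The case against.** **A difference test can support the aim.** A reader might infer that no difference test under the plan could show the MID to be no worse. That goes too far. A significant result favouring the MID, which Aim 2 expects, does show it without a margin. Nor do the documents say that a non-significant result will be claimed as no worse. What stands is narrower: if the difference is not significant, 11.2 gives no basis for the conclusion that 11.1 seeks.

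**Silence is not a wrong choice.** Section 11.2 names a model family, notes that the scores come from the same patients, and does not prescribe independent rows. Clustered cumulative logits belong to that family. This is fair, but the text as written would permit the standard fit.

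**Inflated false positives are not established.** A reader might infer that the plan will produce too many. Three ratings per device is an assumed layout, because 6.3 lists one survey per visit and does not say it is completed once per device. The extremes come from assumed variances, and one rating per device gives only conservatism.

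**There is no fourth MID rating.** Section 3 says "The last QOL evaluation will be at the completion of the patient's radiation treatment", from which a reader might infer a fourth rating of each device. The final visit in 6.4 lists only adverse events, and no MID application is scheduled then. That sentence needs reconciling with 6.3, but it does not support a four-rating analysis.

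**This is a pilot and a secondary endpoint.** The Study Summary and section 2 speak only of assessing comfort and quality of life. That limits the weight of the point. It does not remove it, because 11.1 itself sets out to establish the result.

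**Conclusion.** The point holds in two limited parts.

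- No margin exists on the survey scale, so a non-significant difference could not support the no-worse aim. This follows from the text and needs no assumption.
- The named model, fitted in its standard form to repeated scores from the same patients, generally gives wrong standard errors. The direction depends on a layout that the plan leaves open: about 0.4 to 12% type I error with three ratings per device, conservative with one, and about 5 to 16% with one preference per visit. These sizes are illustrative and rest on assumed variances.

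Clustering or pairing brings the error to about 5% in the layouts where it was examined. Neither can help if the Appendix B form is the only survey, since that form alone cannot give a per-device score. The primary analysis is unaffected. The change should be made, but it is a moderate matter.

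**What to change.** In 11.2:

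- State whether the score is one rating per device or one preference per visit, and confirm that the survey is answered separately for each device if ratings are intended.
- Keep the cumulative logit, with device as a fixed effect and standard errors clustered on patient with a small-sample correction. A paired analysis of patient-level means is an acceptable alternative, but it yields a mean difference rather than an odds ratio. If the score is one preference per visit, cluster the visits on patient.

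In 11.1, either adopt the superiority hypothesis of Aim 2 or state a justified margin on the score scale. Otherwise report the estimate with a 95% CI and make no no-worse claim from a non-significant difference.

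The cost is a few sentences and slightly more analysis work, with no added patients. No new data are needed if ratings are already collected per device; if they are not, the survey itself has to change. The downside is that no worse cannot be claimed from a non-significant difference without a margin, and a tight margin would have low power with 24 patients.
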